**Table 4.2.2.1:1 Restricted medication when coadministered with BI 3011441**

#### 4.2.2.2 Restrictions on diet and life style

Patients should be instructed to avoid exposure to direct sunlight (including sunlamps), to use a sunblock (minimum sun-protection factor 30), and to wear clothing and sunglasses that protect against sun exposure during treatment and for 4 weeks after the last administration of BI 3011441.

The usual restrictions on diet and life style that were already applicable for a given patient before entry into the trial, according to his/her medical condition, have to be continued, if feasible. Grapefruit juice and Sevilla oranges and their juice are not permitted.

#### **4.2.2.3 Contraception requirements**

Women of childbearing potential and men able to father a child must use highly effective methods of birth control per ICH M3 (R2) that result in a low failure rate of less than 1% per year when used consistently and correctly. A list of contraception methods meeting these criteria is provided in the patient information.

### **4.3 TREATMENT COMPLIANCE**

Patients are requested to bring all remaining trial medication including empty package material with them when attending visits.

Based on capsules counts, treatment compliance will be calculated as shown in the formula below. Compliance will be verified by the CRA authorised by the sponsor.

$$\text{Treatment compliance (\%)} = \frac{\text{Number of capsules actually taken} \div 100}{\text{Number of capsules which should have been taken as directed by the investigator}}$$

If the number of doses taken is not between 75-100%, staff will explain to the patient the importance of treatment compliance.

## 5. ASSESSMENTS

### 5.1 ASSESSMENT OF EFFICACY

Tumour response will be evaluated at the site according to RECIST version 1.1 ([R09-0262](#)). The assessment by the Investigator will be the basis for continuation or discontinuation of the trial in an individual patient (in addition to safety).

The patients will be re-evaluated every 8 weeks until the earliest of progressive disease, death or last evaluable tumour assessment before start of subsequent anti-cancer therapy or until the end of the trial. The baseline scan(s) (CT scan and/or MRI according to Investigator's decision) from screening must have been performed within 4 weeks prior to treatment with the trial drug(s) and the Investigator will record the target (5 target lesions in total and maximum 2 per organ) and non-target lesions at baseline in the patient's medical records and in the CRF before the start of treatment. The same method of assessment and the same technique must be used to characterise each reported lesion at baseline and during treatment. In case of suspected (but not otherwise confirmed) bone metastasis at screening, tumour assessment at screening should include a bone scan. If bone lesions are already known or confirmed at screening, correlative imaging (X-ray or CT scan) should be performed. Correlative imaging should then be repeated at each tumour assessment. Lesions in previously irradiated areas may not be considered measurable at baseline unless the lesions occurred after irradiation. Lesion used for biopsies should not be selected for target lesion evaluation. Tumour assessment will be performed at screening (as close as possible to the treatment start and no more than 28 days before the start of trial treatment), at week 8 and every 8 weeks thereafter, and at the EOT visit (if not performed within the last 4 weeks).

If the patient discontinues the trial medication for another reason than progression, the tumour assessment according to RECIST v1.1 will continue every 8 weeks until the last follow-up needed according to protocol (progression, death, lost to follow-up, end of the trial).

### 5.2 ASSESSMENT OF SAFETY

#### 5.2.1 Physical examination

A complete physical examination will be performed at the time points specified in the [Flow chart](#). It includes at a minimum general appearance, neck, lungs, cardiovascular system, abdomen, extremities, and skin.

Measurement of height and body weight will be performed at the time points specified in the Flow chart.

During the physical examination, the patient should be assessed for possible adverse events.

The results must be included in the source documents available at the site.

## 5.2.2 Vital signs

Vital signs will be evaluated at the time points specified in the [Flow Chart](#), prior to blood sampling and trial treatment administration.

This includes body temperature, systolic and diastolic blood pressure and pulse rate (electronically or by palpation count for 1 minute), and saturation of percutaneous oxygen. All except body temperature need to be taken in a seated position after 5 minutes of rest. Oxygen saturation will be measured, if needed. The results must be included in the source documents available at the site.

## 5.2.3 Safety laboratory parameters

Safety laboratory parameters to be assessed are listed in Table 5.2.3: 1. For the sampling time points please see the [Flow Chart](#). All analyses will be performed locally. Patients do not have to be fasted for the blood sampling for the safety laboratory tests.

Clinically relevant abnormal findings as judged by the Investigator will be reported as adverse events (please refer to [Section 5.2.6](#)).

In case the criteria for hepatic injury are fulfilled, a number of additional measures will be performed (please see [Section 5.2.6.1.4](#) and the DILI Checklist provided in the ISF). The amount of blood taken from the patient concerned will be increased due to this additional sampling.

Table 5.2.3:1 Safety laboratory tests

Haematology	Haemoglobin, red blood cell count, haematocrit, mean corpuscular volume, white blood cell count, and differential blood count (preferably expressed in absolute values), and platelets.
Biochemistry	Glucose, sodium, potassium, chloride, calcium, creatinine, phosphate, venous bicarbonate ( $\text{HCO}_3$ ), AST, ALT, alkaline phosphatase, lactate dehydrogenase, lipase, bilirubin (direct and indirect bilirubin in case of elevated total bilirubin values), total protein, albumin, urea nitrogen, uric acid and creatinine kinase (CK; if CK is elevated, then myoglobin and creatine kinase myocardial band (CK-MB) [cardiac] should also be measured; if a patient has signs/symptoms of myocardial ischemia and CK elevation, then CK-MB, Troponin I or T should also be reactively tested).  Note: Creatinine can be assessed by any of these methods: CREE (enzymatic serum creatinine assay), CREJIDMS (isotype dilution mass spectrometry (IDMS) standardized Jaffe), or CREJ (non IDMS standardized Jaffe).
Coagulation	Activated partial thromboplastin time (aPTT) or prothrombin time (PT) (expressed either in seconds or as percentage)
Urine	Urine (pH, glucose, erythrocytes, leukocytes, protein, and nitrite) will be analysed by dipstick (semi-quantitative measurements).

Table 5.2.3:1 Safety laboratory tests (cont.)

Pregnancy test	A beta human chorionic gonadotropin ( $\beta$ -HCG) pregnancy test in serum will be performed for women of childbearing potential at screening. Thereafter, this test may be done in serum or urine on Day 1 of each cycle, at the EOT visit, and at the 30-day safety follow-up visit.
Virology (screening)	Hepatitis B (HBs-Ag, and if HBs-Ag is negative anti-HBs, anti-HBc antibodies and HBV DNA will be measured) and hepatitis C (PCR)

If laboratory safety investigations have been performed  $>72$  hours prior to the first trial treatment, the results of the new safety laboratory investigations performed within 72 hours of first treatment must be available to reconfirm eligibility.

#### 5.2.4      **Electrocardiogram**

Standard 12-lead (I, II, III, aVR, aVL, aVF, V1 - V6) resting electrocardiograms (ECGs) will be digitally recorded in triplicate (3 single ECGs within a maximum period of 5 minutes) and performed for each patient at various time points during the trial according to the appropriate Flow Chart and Appendix 10.1. This will include triplicate readings at every PK sampling time point during Cycle 1 on Days 1, 15, and 16.

All ECGs will be obtained after the patient has been resting supine for at least 5 minutes prior to the indicated times. All ECGs should be recorded with the patient in the same physical position.

Electrocardiogram machines will be provided to facilitate central retrospective readings. Before trial start, the trial sites will be trained for the proper use of the equipment and transfer of the electronic data to the vendor. While all ECGs will be transmitted to the central vendor, they will be analysed only after PK analysis points to a  $t_{max}$ .

ECGs may be repeated for quality reasons and the repeated recording used for analysis. If necessary, additional ECGs may be recorded for safety reasons.

The ECG recordings must be analysed and checked for abnormality by the Investigator (or designated physician) who will also calculate the QTcF value for each time point as the mean of the 3 ECGs. Clinically relevant abnormal findings will be reported either as baseline condition (if identified at the screening visit) or otherwise as adverse events and will be followed up and/or treated as medically appropriate. CTCAE version 5.0 will be used for the grading of prolonged QTcF intervals. Dated and signed printouts of ECG with findings should be documented in patient's medical record.

In case of related ECG changes and whenever the Investigator deems necessary, additional ECG monitoring will be performed in the respective and later courses of treatment. To allow for a heart rate correction of QT intervals the QT intervals will be matched to the preceding RR intervals using at least QTcF (Fridericia's formula  $QTcF = QT/RR^{-1/3}$ ) and QTcB (Bazett's formula  $QTcB = QT/RR^{-1/2}$ ).

Proprietary confidential information © 2020 Boehringer Ingelheim International GmbH or one or more of its affiliated companies

In case of QTcF prolongation to >500 ms (mean of 3 ECGs) AFTER receiving therapy, the Investigator will initiate further ECG monitoring and diagnostics (e.g., check electrolytes and check concomitant therapy that may be contributing to QTcF prolongation) and if required provide adequate treatment according to medical standards. The patient will be discharged from the investigational site only after resolution of ECG findings as assessed by the Investigator.

In case of occurrence of symptoms suggestive of arrhythmia related to QTcF prolongation, a cardiologic evaluation will be performed, and treatment will be provided according to medical standards at the discretion of the Investigator.

In order not to confuse an ECG recording, PK samples should be taken after performing the ECG.

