as: Blood pressure measured in a rested and relaxed condition, where systolic BP  $\geq 140$  mmHg, or diastolic BP  $\geq 90$  mmHg, with or without medication.

9. Left ventricular ejection fraction (LVEF)  $< 50\%$ .
10. Baseline QT interval corrected for heart rate using Fridericia's formula (QTcF)  $> 470$  msec or congenital long QT syndrome
11. Previous or concomitant malignancies at other sites, except effectively treated
  - Non-melanoma skin cancers
  - Carcinoma *in situ* of the cervix
  - Ductal carcinoma *in situ*
  - Other malignancy that has been in remission for more than 3 years and is considered to be cured.
12. Leptomeningeal carcinomatosis.
13. Presence or history of uncontrolled or symptomatic brain metastases, unless considered stable by the investigator and local therapy was completed. Use of corticosteroids is allowed if the dose was stable for at least 4 weeks. Inclusion of patients with newly identified brain metastasis/es at screening will be allowed if patients are asymptomatic.
  - Patients who have resected brain metastases, or have received radiation therapy that finished at least 4 weeks (whole brain radiation) or 2 weeks (stereotactic body radiotherapy) prior to treatment of the trial are considered eligible if they meet all of the following criteria:
    - a) Residual neurological symptoms CTCAE grade  $\leq 2$
    - b) Are taking stable doses of dexamethasone, if applicable
    - c) Follow-up magnetic resonance imaging (MRI) shows no new lesions
14. Known pre-existing interstitial lung disease
15. Known active hepatitis B infection (defined as presence of Hep B sAg and/or Hep B DNA), active hepatitis C infection (defined as presence of Hep C RNA)
16. Active infectious disease which puts the patient at increased risk in the opinion of the investigator
17. Any history or presence of uncontrolled gastrointestinal disorders that could affect the intake and/or absorption of the study drug (e.g. nausea, uncontrolled vomiting, Crohn's disease, ulcerative colitis, chronic diarrhoea, malabsorption) in the opinion of the investigator.
18. Patients not expected to comply with the protocol requirements or not expected to complete the trial as scheduled (e.g. chronic alcohol or drug abuse or any other condition that, in the investigator's opinion, makes the patient an unreliable trial participant).

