7.8.4 ECG

Clinically relevant abnormal findings will be reported as adverse events. Scatterplot of the BI 3011441 plasma concentration against the following individual QTcF values will be provided. Scatterplots of baseline and post QTcF against the following individual QTcF values will be provided.

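### Protocol 5.2.4 prints the Fridericia and Bazett formulas with the exponent sign reversed; applied as printed, QTcF would be too low above 60/min and too high below it

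*Protocol*

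**What the plan says.** Protocol Section 5.2.4 states its aim as follows: "To allow for a heart rate correction of QT intervals the QT intervals will be matched to the preceding RR intervals". It then prints "Fridericia's formula $QTcF = QT/RR^{-1/3" for Fridericia and "Bazett's formula $QTcB = QT/RR^{-1/2" for Bazett (the closing brackets are cut off in these extracts). It gives no unit for RR. The same section assigns the calculation to the Investigator or a designated physician, "who will also calculate the QTcF value for each time point as the mean of the 3 ECGs".

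QTcF is used in four places:

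- **Eligibility.** Protocol 3.3.3, exclusion criterion 10, with the same rule in the Synopsis: "Baseline QT interval corrected for heart rate using Fridericia's formula (QTcF) $> 470$ msec or congenital long QT syndrome". The method is named, but no formula is given and Section 5.2.4 is not cited.
- **On-treatment monitoring.** Protocol 5.2.4: "In case of QTcF prolongation to >500 ms (mean of 3 ECGs) AFTER receiving therapy", the Investigator starts further ECG monitoring and diagnostics.
- **Grading.** Protocol 5.2.4 grades prolonged QTcF by CTCAE version 5.0.
- **Analysis.** SAP 7.8.4: "Scatterplot of the BI 3011441 plasma concentration against the following individual QTcF values will be provided". The SAP gives no QTcF formula of its own.

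**The concern.** A heart rate correction has to lengthen QT at fast rates and shorten it at slow rates. The printed expressions do the opposite. The formula is not background text: it stands in the section that tells the site to compute the value, and nothing elsewhere in the protocol or SAP overrides it.

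QT prolongation is the first risk in Protocol Table 1.4.2:1, and the mitigation given there is the >470 msec exclusion together with frequent ECGs. If a site took the printed formula at its word, eligibility, the >500 ms trigger and the grade of a QTcF event would rest on a number whose error depends on heart rate.

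**Working it through.** **Inputs.** The two printed formulas and the 470 and 500 ms limits come from the protocol. The documents give no heart rates, no raw QT values and no RR unit. The QT and heart rate pairs below are therefore illustrative assumptions, and RR is taken in seconds as 60 / heart rate.

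**Algebra.**

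- Standard Fridericia: QT / RR^(1/3), which is the same as QT × RR^(-1/3).
- As printed: QT / RR^(-1/3) = QT × RR^(1/3).
- Ratio of printed to standard: RR^(1/3) / RR^(-1/3) = RR^(2/3). It equals 1 only at RR = 1 s (60/min). It is 0.76 at 90/min and 1.21 at 45/min.
- If raw QT varies as RR^(1/3), which is what a cube-root correction presumes, the standard form removes that dependence. The printed form leaves a dependence on RR^(2/3), so the exponent is doubled instead of cancelled.

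**Worked values (ms).**

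| Assumed QT | Rate (/min) | RR (s) | RR^(1/3) | Standard: QT ÷ RR^(1/3) | Printed: QT × RR^(1/3) | Limit | Standard | Printed |
|---|---|---|---|---|---|---|---|---|
| 420 | 90 | 0.667 | 0.874 | 481 | 367 | 470 | over | under |
| 400 | 100 | 0.600 | 0.843 | 474 | 337 | 470 | over | under |
| 440 | 45 | 1.333 | 1.101 | 400 | 484 | 470 | under | over |
| 440 | 100 | 0.600 | 0.843 | 522 | 371 | 500 | over | under |
| 480 | 50 | 1.200 | 1.063 | 452 | 510 | 500 | under | over |

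**The same thing seen from the limits.** The printed value reaches a limit L when the standard QTcF equals L / RR^(2/3).

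| Rate (/min) | Standard QTcF when printed value = 470 | Standard QTcF when printed value = 500 |
|---|---|---|
| 50 | 416 | 443 |
| 60 | 470 | 500 |
| 75 | 545 | 580 |
| 100 | 661 | 703 |

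**Bazett.** The printed form multiplies by RR^(1/2). At 100/min the factor is 0.775, where the standard factor is 1 / 0.775 = 1.291. It is reversed in the same way.

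**The case against.** The algebra is not in dispute; the effect on the trial is. A reader might infer that the 470 and 500 ms limits will pass patients with long QT at fast rates and flag normal patients at slow ones. The documents do not support that, for these reasons:

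- Exclusion criterion 10 names Fridericia and does not point to Section 5.2.4. Someone who follows the named method gets the intended value.
- ECGs are recorded digitally on machines supplied for the trial, with site training. Having the Investigator take the mean of three ECGs can be read as averaging three QTcF values already available, not as working each out from RR. The text does not settle which.
- Central readings are to comply with ICH E14.
- Other safeguards do not depend on the formula. Congenital long QT syndrome is excluded whatever the QTcF, drugs that might prolong QT are prohibited (Protocol 4.2.2.1), and symptoms suggesting a related arrhythmia lead to a cardiologic evaluation.

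A reader might also infer damage to the DLT count, and so to the MTD, or to the concentration-QTcF plots. The DLT list in Protocol 5.2.6.3 has no QTcF item, so QTcF could enter only through general clauses such as the one on Grade 3 or higher non-haematologic toxicity. SAP 7.8.4 does not say that its QTcF values come from the printed formula, and Protocol 7.3.5 foresees analysis of centrally evaluated ECGs. Neither effect is shown.

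Finally, the text was machine-read from PDF and the fault is a minus sign in a superscript. The compliance formula in Protocol 4.3 also shows a doubtful operator (division by 100 where a percentage needs multiplication), so a systematic reading fault cannot be excluded. The same sign in both formulas makes a random one less likely.

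What stands against this: central reading is retrospective and is done only after the PK analysis points to a tmax, so it does not protect eligibility or on-treatment decisions when they are made. For those the site value counts, and the only formula given to the site is the printed one.

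**Conclusion.** The printed formulas are wrong as written, subject to confirming the minus signs on the source page. They contradict both the methods they name and the stated purpose of the section. The most likely explanation is a misprint.

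The consequence is conditional. Where the formula is applied literally, QTcF is wrong by the factor RR^(2/3) at every rate except 60/min: about 24% too low at 90/min (ratio 0.76) and 21% too high at 45/min (ratio 1.21). The >470 msec exclusion, the >500 ms trigger and the CTCAE grading could then misclassify patients in either direction. These sizes assume RR in seconds and illustrative heart rates and QT values. They show what the misprint could do, not how many patients it would affect.

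The documents do not show that any site, machine or vendor would use the printed form, and they do not show an effect on DLTs, the MTD or the SAP 7.8.4 plots. The point is still worth correcting, because this is the only written definition of a safety variable that the site is told to calculate. The 470 and 500 ms limits themselves are not questioned here.

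**What to change.** 1. Check the two exponents in Protocol 5.2.4 against the source page.
2. If the minus signs are there, print QTcF = QT/RR^(1/3) and QTcB = QT/RR^(1/2), with RR in seconds.
3. State that this one QTcF definition applies to exclusion criterion 10, the >500 ms rule, CTCAE grading and SAP 7.8.4.
4. Confirm with the sites and the ECG vendor that the standard form is the one in use.

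The cost is a short text correction, one cross-referencing sentence and one query. No threshold, visit, procedure or clinical rule changes. If the query did find literal use, the affected values could be recalculated, since the ECGs are recorded digitally and all are sent to the central vendor.

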#### Centralised ECG evaluation

Abnormalities detected during centralised ECG evaluation will not necessarily qualify as AEs. In case of clinically relevant abnormalities (e.g., heart blocks or large changes in interval duration) the ECG core laboratory may contact the Investigator and vice versa. Centrally assessed ECGs will comply with the ICH E14 guidance document and supplements ([R05-2311](#), [R13-0801](#), [R13-4095](#)) as well as the FDA requirements for annotated digital ECGs ([R09-4830](#)).

#### **5.2.5 Other safety parameters**

##### ECOG

The ECOG performance status will be assessed at the times indicated in the [Flow Chart](#).

##### Ophthalmological assessments

Patients are required to have a standard ophthalmologic exam performed by an ophthalmologist at baseline, at each defined timepoint (see Flow Chart) and as clinically indicated. The exam will include indirect fundoscopic examination, visual acuity, visual field examination, tonometry and slit lamp examination with special attention to retinal abnormalities that are predisposing factors for RVO or retinopathy.

In addition, it is recommended that patients have baseline color fundus photographs to document baseline appearance. In patients with clinical suspicion of RVO or retinopathy, additional color fundus photographs are recommended, and fluorescein angiography and/or optical coherence tomography are recommended.

##### Echocardiography

Echocardiography will be performed to assess cardiac ejection fraction and other abnormalities if applicable as indicated in the Flow Chart. Additional echocardiography assessments may be performed if clinically indicated.

## 5.2.6 Assessment of adverse events

### 5.2.6.1 Definitions of AEs

#### 5.2.6.1.1 Adverse event

An AE is defined as any untoward medical occurrence in a patient or clinical investigation subject administered a medicinal product and which does not necessarily have to have a causal relationship with this treatment.

An AE can therefore be any unfavourable and unintended sign (including an abnormal laboratory finding), symptom, or disease temporally associated with the use of a medicinal product, whether or not considered related to the medicinal product.

The following should also be recorded as an AE in the CRF and BI SAE form (if applicable):

- Worsening of the underlying disease or of other pre-existing conditions, see [section 5.2.6.2.4](#) for further detail.
- Changes in vital signs, ECG, physical examination, laboratory test results, ophthalmological assessment and echocardiography if they are judged clinically relevant by the investigator.

If such abnormalities already exist prior to trial inclusion, they will be considered as baseline conditions and should be collected in the eCRF only.

